# 8 STUDY OBJECTIVES

# 8.1 Safety and Tolerability Objective:

Overall, the primary objective is to describe the safety, tolerability and exposure-toxicity relationship of DZD given over 16 weeks in combination with standard-dose BDQ, DLM and MXF compared to standard-dose BDQ, DLM and MXF alone.

The aim is to identify the optimal dose of DZD to be used in subsequent studies that provides the best **efficacy at acceptable safety** of the drug when given daily over 4 months in patients with newly diagnosed, uncomplicated, smear-positive, drug-sensitive, pulmonary tuberculosis.

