# 9 TRIAL ENDPOINTS

#### 9.1 Primary Endpoints

#### 9.1.1 Primary Safety endpoint

Participants will be regularly assessed for AEs during treatment and follow-up phase, including assessments of vital signs, physical examination, weight, detailed neurological examination, colour vision and visual acuity tests, 12-lead ECGs and routine clinical laboratory tests (including chemistry, haematology and urinalysis data).

The safety of DZD will be investigated by evaluation of:

• Proportion of patients experiencing expected oxazolidinone class toxicities, defined as peripheral or optical neuropathy, or incident leukopenia, anemia or thrombocytopenia, or adverse events in line with tyramine pressor response, all of Grade 2 or higher, possibly, probably or definitely related to DZD

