# 12.2 Study drug dosage and administration

The experimental and control treatment as described above will be administered daily for 16 weeks (see Table 1. Daily Dosing of Study Medication), together with food.

- Bedaquiline: will be dosed as per the licensed dose: 400 mg orally once daily for the first 14 days, then 200 mg three times a week.
- Delamanid: will be dosed as per the licensed dose: 200 mg orally in two daily doses of 100 mg.
- Moxifloxacin: will be dosed as per the licensed dose: 400 mg orally once daily
- Delpazolid not licensed:
  - Dose: will be according to randomization to dosing arm:
    - Arm 1: 15 participants will receive 0 mg of DZD
    - Arm 2: 15 participants will receive 400 mg DZD orally once daily
    - Arm 3: 15 participants will receive 800 mg DZD orally once daily
    - Arm 4: 15 participants will receive 1200 mg DZD orally once daily
    - Arm 5: 15 participants will receive 800 mg DZD orally twice daily

The daily dose of study drug for participants will be dependent on the subjects' experimental arm as shown in the following table:

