# **13.6 Methods of avoiding bias**

This study will be open-label, patients and physicians will be aware of treatment allocation. To ensure unbiased assessment of efficacy endpoints, the personnel assessing patients' outcomes, like the microbiology laboratory staff or the sponsor medical expert discussing the possibility of recurrent disease, will remain blinded to treatment assignment throughout the whole study. Every effort will be made to maintain this blinding.

Further, there will not be any cumulative summary of study data by randomized treatment arms generated, except for data to be provided to the independent data safety monitoring board (DSMB) by the unblinded statistician. Such analysis may not be distributed outside of the DSMB.

Determination of MICs for the experimental treatment allocated to the patients will only be made after all other assessments of patient samples have been completed in the respective laboratory or will be done at a different specialised laboratory.

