 Neuropathy stopping criterion: Participants will stop treatment with DZD in case they develop clinically significant signs of motor or sensory neuropathy, i.e. loss of muscle strength, loss of sensation, loss of vibration sensitivity, or loss of visual acuity or colour vision.

In this case, treatment with BDQ, DLM and MXF may continue as scheduled. Since neuropathy may be associated to MXF in rare events, a discontinuation of MXF may be advised in severe cases of neuropathy or if neuropathy does not improve after DZD is discontinued.

• Hypertension (tyramine pressor effect) stopping criterion:

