# 14.5 Assessment of Causality

The Investigator will review each AE and assess its relationship to study treatment based on all available information at the time of the completion of the CRF.

Each sign or symptom reported will be graded on a 5-point severity scale (see below). Additionally, the date and time of onset, relationship to the study medication, duration, action taken, and outcome (resolved, improved, unchanged, worse, fatal, or unknown (lost to follow-up) of each event will be noted.

Relationship	Description	Event Type (if Serious)	
Unrelated	There is no evidence of any causal relationship	Unrelated SAE	
Unlikely	There is little evidence to suggest there is a causal relationship (e.g. the event did not occur within a reasonable time after administration of the trial medication). There is another reasonable explanation for the event (e.g. the patient's clinical condition, other concomitant treatment).	Unrelated SAE	
Possible	There is some evidence to suggest a causal relationship (e.g. because the event occurs within a reasonable time after administration of the trial medication). However, the influence of other factors may have contributed to the event (e.g. the patient's clinical condition, other concomitant treatments).	SAR	
Probable	There is evidence to suggest a causal relationship and the influence of other factors is unlikely.	SAR	
Definitely	There is clear evidence to suggest a causal relationship and other possible contributing factors can be ruled out.	SAR	

The following definitions for rating attribution/causality will be applied:

Factors to be considered in judging relatedness include:

- The temporal sequence from drug administration.
- Recovery on discontinuation (de-challenge), recurrence on re-administration (rechallenge).
- Underlying, concomitant, intercurrent disease.
- Concomitant medication or treatment.
- Known response pattern for the classes of drug the participant is receiving
- Exposure to physical and/or mental stresses.
- The pharmacology and PK of the medication used.

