## 14.8 Adverse event reporting

Adverse events will be recorded by the investigator from the time a participant signs the informed consent form.

Any AE (serious or non-serious) observed by the investigator or reported by the subject will be recorded in the source data and on the Adverse Event electronic case report form (eCRF). The Investigator will review each AE and assess its relationship to the study treatment based on all available information at the time of the visit. The following information will be recorded for each AE reported:

- Diagnosis of the AE, if possible. In the case where an overall diagnosis cannot be made, each specific sign and/or symptom will be recorded as individual AEs; where possible the wording in the CTCAE should be used.
- Date of onset
- Stop date (duration) if applicable
- Severity (grade)
- Action taken with IMP/non-IMP study drugs
- Other action taken
- Outcome
- Relationship to IMP/non-IMP study drugs
- Occurrence
- Seriousness

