3.1. Safety and Tolerability Objective

To describe the safety, tolerability and exposure-toxicity relationship of delpazolid (DZD) given over 16 weeks, in combination with standard-dose BDQ, DLM and MXF, compared to standard dose BDQ, DLM and MXF alone.

The aim is to identify the optimal dose of DZD to be used in subsequent studies that provides the best efficacy at acceptable safety of the drug when given daily over 4 months in patients with newly diagnosed, uncomplicated, smear-positive, drug-sensitive, pulmonary tuberculosis.

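### Counting only DZD-related toxicities fixes Arm 1 at zero, so the primary safety endpoint cannot describe safety against BDM alone

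*Protocol*

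**What the plan says.** Protocol 9.1.1 and SAP 5.1.1 define the primary safety endpoint as the proportion of patients with an expected oxazolidinone class toxicity: peripheral or optical neuropathy, incident leukopenia, anaemia or thrombocytopenia, or events consistent with a tyramine pressor response. Events count only if they are "all of Grade 2 or higher, possibly, probably or definitely related to DZD".

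The safety objective is comparative. Protocol 8.1 describes safety, tolerability and exposure-toxicity of DZD plus BDM "compared to standard-dose BDQ, DLM and MXF alone", and SAP 3.1 says the same ("compared to standard dose BDQ, DLM and MXF alone").

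Protocol 12.2 sets the control arm: "Arm 1: 15 participants will receive 0 mg of DZD". No placebo is described. Protocol 13.6 states: "This study will be open-label, patients and physicians will be aware of treatment allocation". Protocol 14.5 gives causality to the investigator: "The Investigator will review each AE and assess its relationship to study treatment based on all available information".

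The planned safety analysis is descriptive tabulation by arm (SAP 13.2), with no test or margin.

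**The concern.** An endpoint conditional on attribution to DZD has no valid cases in an arm that gets no DZD. Any contrast with Arm 1 is then just the DZD arm's own attributed proportion.

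Background events do exist in principle. Protocol 13.10 accepts one source that is common to every arm: "Since neuropathy may be associated to MXF in rare events". The entry criteria in Protocol 10.4 admit some HIV-positive patients, and haemoglobin down to 7.0 g/dl, so cytopenias with other causes are plausible.

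Attribution can push the result either way. Protocol 14.5 lists the known response pattern of the drug class as a causality factor, which favours blaming DZD for exactly these events. Protocol 4.2 voices the hope that the main class toxicities will not be seen with DZD, which could favour under-attribution.

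No hypothesis test is at risk, so the harm is to interpretation. These data are meant to support choosing a dose with acceptable safety (Protocol 5 and 8.1), and a structural zero beside the DZD proportions is a misleading reference. Comparisons among the four DZD arms escape the structural zero, but they still rest on attribution by investigators who know the dose.

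**Working it through.** The documents give no rate, power or precision figure for this endpoint, so there is no stated figure to reproduce. The check is one of definition, followed by an illustration of size.

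**1. Arm 1 under the definition.** Qualification needs at least possible relatedness to DZD. The dose is 0 mg and the attributing investigator knows this. The count is 0 of 15 whatever happens to the patients. Neither document says in words that Arm 1 is scored zero; this is an inference, but any other count would be an attribution error.

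**2. Size of the distortion.** Let b be the background rate of these Grade 2 or higher events, d the true excess caused by DZD, and a the share of events in a DZD arm attributed to DZD. None of the three is in the documents; the ranges below are assumptions.

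- The endpoint shows a(b + d) in the DZD arm and 0 in Arm 1.
- The true difference is d.
- Distortion = a(b + d) − d = ab − (1 − a)d.

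| b | d (points) | a | Endpoint shows | True | Distortion |
|---|---|---|---|---|---|
| 5% | 0 | 0.5 | 2.5 | 0 | +2.5 |
| 20% | 0 | 1 | 20 | 0 | +20 |
| 10% | 20 | 0.5 | 15 | 20 | −5 |
| 5% | 20 | 0.5 | 12.5 | 20 | −7.5 |

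Over b = 5–20%, a = 0.5–1 and d = 0–20 points, the range is −7.5 to +20 points.

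**3. What an all-cause count would show in Arm 1.** Expected events are 15b, and the chance of none is (1 − b)^15.

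| b | Expected events in 15 | Chance of 0/15, all-cause | Chance of 0/15, as defined |
|---|---|---|---|
| 5% | 0.75 | 46% | 100% |
| 10% | 1.5 | 21% | 100% |
| 20% | 3.0 | 3.5% | 100% |

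With b = 10%, d = 0 and a = 1, a DZD arm has a 1 − 0.9^15 = 79% chance of at least one endpoint case with no drug effect at all.

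**4. An invented example.** With 4/15 in a DZD arm (exact 95% CI 7.8 to 55.1%):

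- Against the fixed 0/15: +26.7 points, Newcombe 95% CI 0.9 to 52.0. This interval treats the zero as observed, which it is not. It is shown only because a reader could easily compute it.
- Against 2/15 (exact 95% CI 1.7 to 40.5%), had two Arm 1 events been counted: +13.3 points, −15.8 to 40.4.

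**5. Whether another planned output fills the gap.**

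- Secondary endpoints (Protocol 9.2.1, SAP 5.2.1) cover all AEs, Grade 3 or higher AEs, and AEs related to any study drug. None is limited to the class toxicities at Grade 2 or higher.
- SAP appendix Table 3.4.1 gives grades across all event types. Table 3.4.2 gives event types across all grades.
- The haematology shells, Tables 3.2.17 and 3.2.18, are group means under the headings platelet count and haemoglobin. The second carries the platelet title, and there is no leukocyte table.
- There is no shell for the primary safety endpoint, with or without the relatedness condition.

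**6. A related wording point.** SAP 13.1.2 starts treatment-emergent AEs at administration of the IMP. Under Protocol 7 only DZD is the IMP, so read literally Arm 1 has no treatment-emergent events. Protocol 14.2 registers AEs from the first dose of study drugs, and SAP 13.1.2 also plans whole-study tables, so Arm 1 data are not lost.

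**The case against.** The best counter-argument is that the comparison belongs to the objective as a whole and need not be carried by this endpoint. No section assigns the contrast with Arm 1 to it alone, and a drug-attributed endpoint is a recognisable choice in a descriptive dose-ranging trial. SAP 13.1.2 plans AE summaries by arm, preferred term and maximum severity. SAP 13.2 tabulates worsening from baseline on laboratory, neurological, vision and vital-sign variables. Both cover Arm 1 without attribution, and the SAP says its shells are guidance that may be updated.

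This narrows the gap but does not close it. Counts by preferred term cannot be summed into a per-patient composite without double counting, and worsening on a variable is not a Grade 2 or higher event. The endpoint labelled primary remains the one that cannot be compared with control.

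Three further objections have weight:

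- The rates in the illustration are assumed. The protocol's only cue is that neuropathy from MXF is rare, which by itself does not support the upper end of the range.
- Nothing shows that Arm 1 will be printed as 0/15 rather than as not applicable, although tabulating a binary variable by arm leads naturally to a zero.
- An all-cause composite needs a list of preferred terms and a rule for what is incident. That is true, but the DZD-related version needs the same list and rule.

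**Conclusion.** The point holds. Arm 1 is zero by construction, so the primary safety endpoint cannot support the descriptive comparison with BDM alone that both documents state as the objective. The conclusion rests on the definition, the 0 mg arm and open-label attribution, and on no assumed rate.

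The size is illustrative: +2.5 to +20 points when DZD has no effect, and −7.5 to +20 points when a true excess of up to 20 points is allowed, under the assumed ranges for background and attribution. The defect is confined to this endpoint; the wider safety data still describe Arm 1. It should be fixed, because it affects a primary endpoint and the repair is cheap.

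**What to change.** Amend the SAP before the partial database lock:

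- Add the Grade 2 or higher class-toxicity composite regardless of attributed cause, per patient, in all five arms. Give each arm's exact 95% CI and its difference from Arm 1 with a 95% CI. Name this version as the one used for the comparison with BDM alone.
- Keep the DZD-related version beside it as the protocol's primary endpoint, and state that Arm 1 cannot contribute events to it.
- Add one table shell showing both, with the preferred terms and the rule for incident events that both versions need.
- Define treatment-emergent AEs from the first dose of any study drug.

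The cost is SAP wording and one table. No new data are needed: Protocol 14.8 states "Any AE (serious or non-serious) observed by the investigator or reported by the subject will be recorded in the source data", with grade and relationship recorded for each event. The protocol endpoint need not be replaced.

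Two drawbacks remain. Background events add noise, and with 15 per arm the intervals will be wide. The judgement of whether an abnormality is clinically significant enough to be an AE (Protocol 14.2 and 14.10) is still made by investigators who know the arm.

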#### 9.1.2 Primary Efficacy Endpoint

The efficacy of DZD will be evaluated by measuring the change in mycobacterial load over time on treatment as quantified by time to positivity in BD MGIT 960® liquid culture described by non-linear mixed-effects methodology

#### 9.2 Secondary Endpoints

#### 9.2.1 Secondary safety endpoints

- All adverse events
- Adverse events of Grade 3 severity or higher
- Adverse events possibly, probably or definitely related to study drugs
- Treatment discontinuations or interruptions related to adverse events/serious adverse events
- Frequency, severity and type of ECG alterations
- Changes in ECG intervals of PR, RR, QRS, QT, Fridericia-corrected QT [QTcF]

- Proportion of participants with QTcF > 500ms in ECGs on treatment
- Proportion of participants with a prolongation of QTcF > 60ms in ECGs of grade 3 and above as defined under 14.6 *Table 2*

#### 9.2.2 Secondary Efficacy Endpoints

Further efficacy of DZD will be evaluated by assessment of:

- Proportion of patients who suffer relapse, defined as recurrent disease caused by a strain identical to the baseline isolate, within 12 months post randomisation, out of patients completing 16 weeks of therapy and achieving stable culture conversion to negative (SCC) as defined below by week 08, with no positives to follow by the week 16 visit.
- Time to recurrent TB, and to relapse, within 12 months post randomisation
- Time to stable sputum culture conversion (SCC) to negative on liquid media (defined as two negative cultures without an intervening positive culture). Time will be measured as time on treatment until the first negative culture.
- Proportion of participants who achieved SCC at each time point during treatment
- Proportion of participants with negative sputum culture on solid media at WK 08 and other timepoints
- Proportion of participants developing drug resistance among those not converting to negative culture

#### 9.2.3 Pharmacokinetic Endpoints

A population PK model will be developed for DZD. The following secondary parameters will be derived for DZD, for BDQ, DLM and their main metabolites, and for MXF:

- Area under the plasma concentration curve from morning dosing to 24 hours (AUC 0-24) on day 14 (WK02)
- The observed maximum concentration (Cmax) on day 14
- Time to reach Cmax (Tmax) on day 14
- The minimum observed plasma concentration (Cmin) at day 14 (24 hours following the last dose for QD and 12 hours following the last dose for BID)
- Apparent oral clearance (Cl/F)
- Apparent volume of distribution (Vd/F)
- Terminal half-life (t1/2)

Analyses may be limited by available budget, which may lead to parameters for certain drugs not being reported.

#### 9.2.4 Mycobacteriology Identification and Characterization Endpoint

Sputum cultures from various timepoints during the study will be assessed as follows:

- Minimum inhibitory concentrations (MIC) of BDQ, DLM, MXF, DZD of the infecting strain, at baseline and on representative isolate(s) grown at or after WK08, if any.
- Frequency of acquired mutations in the infecting strain over treatment by whole genome sequencing
- Comparison between bacterial strain causing recurrent disease, and the strain at baseline by whole genome sequencing, to discriminate relapse from re-infection.

These assessments will be performed dependent on availability of lab capacity and budget, so may not be completed for all possible timepoints.

#### 9.2.5 Exploratory Endpoints

The following exploratory endpoints will be analysed depending on laboratory capacity, availability of test kits and budgets permit and may not be tested in all trial sites:

- Rate of change of bacterial load measured by molecular bacterial assay (MBLA) during treatment
- Time to stable conversion to negative in MBLA (defined as two negative MBLAs without an intervening positive)
- Rate of change in bacterial load measured by quantification of sputum lipoarabinomannan (LAM) during treatment

These assessments will be performed dependent on availability of lab capacity and budget.

# 10 TRIAL DESIGN

#### 10.1 Summary

This will be an open label Phase IIb, randomized, controlled, dose-finding, multi-centre study in participants with newly diagnosed, smear positive, uncomplicated, DS pulmonary TB.

#### **10.2** Trial population

Participants will be randomized to one of five arms containing a BDM backbone with different doses of DZD, ranging from 0mg DZD (no DZD present in the regimen) up to 1,600mg (800mg BD). 75 participants will be randomized into this study, with 15 participants per arm.

In the case of unforeseen delays or a rate of dropouts or non-evaluable participants that is higher than anticipated, it may be necessary to recruit more participants than planned into the entire study (see sample size considerations, Chap. 15.1).

Participants will be randomised by centralized allocation, using a probabilistic minimisation algorithm, which will stratify participants by bacterial load in sputum as measured by GeneXpert cycle threshold, site and HIV status.

Participants will visit the study clinic on a weekly basis for sputum collection, safety monitoring and receipt of study medication.

After the completion of 16 weeks of experimental treatment, participants in the experimental arms, who did not achieve two successive negative liquid media cultures with the first at or before WK08, with no positives to follow by the week 16 visit, will be referred to their local health care facility to complete their course of anti-TB treatment according to the national TB program.

#### **10.3** Inclusion Criteria

Participants are required to meet **all** the following criteria in order to be randomized:

- 1. Provide written, informed consent prior to all trial-related procedures including HIV testing.
- 2. Male or female, aged between 18 and 65 years, inclusive.
- 3. Body weight (in light clothing and with no shoes) between 40 and 90 kg, inclusive.
- 4. Newly diagnosed, previously untreated, drug susceptible pulmonary TB: presence of MTB complex and rapid molecular tests result confirming susceptibility to RIF and INH such as GeneXpert and/or HAIN MTBDR *plus*.
- 5. A chest X-ray (no older than 2 weeks) which, in the opinion of the Investigator, is consistent with TB.
- 6. Sputum positive on microscopy from concentrated sputum for acid-fast bacilli on at least one sputum sample (at least 1+ on the IUATLD/WHO scale).
- 7. The participant is willing to forgo consumption of foods high in tyramine for the period of taking study medication (See Appendix, section 20.2, page 95).
- 8. The participant is either unable to conceive/father children AND/OR his/her partner is unable to conceive/father children AND/OR they will consent to be using effective methods of contraception when engaging in heterosexual intercourse, as defined below:
  - a. Non-childbearing potential:
    - Female participant/sexual partner of male participant: Bilateral oophorectomy, and/or hysterectomy or bilateral tubal ligation more than 12 months ago and/or has been postmenopausal with a history of no menses for at least 12 consecutive months
    - ii. Male participant/sexual partner of female participant: Vasectomised or has had a bilateral orchidectomy minimally three months prior to screening
    - iii. Male participants having a pregnant female partner or a male sexual partner: At least one barrier method has to be used in this case.
  - b. Effective contraception methods:

- i. Female participants: Two methods, including methods that the patient's sexual partner(s) use. At least one must be a barrier method. Contraception must be practised for at least until 12 weeks after the last dose of DZD.
- Male participants: Two methods, including methods that the patient's female sexual partner(s) use. At least one must be a barrier method.
   Effective contraception must be ensured for at least 16 weeks after the last dose of DZD.

Note: hormone-based contraception alone may not be reliable when taking RIF during continuation phase; therefore, hormone-based contraceptives alone cannot be used by female participants/female partners of male participants to prevent pregnancy.

